2.1 Intent-to-Treat Population

All patients randomized into the study will be included in the ITT population, if at least one dose or a part of Nanocort IV/Placebo infusion or Depo-Medrol/placebo IM injection was administered and at least one post-baseline efficacy measurement was performed.

Patients will be analyzed within the original treatment group they were randomized to. All analyses will be completed for the ITT population. The main analyses for assessment of study success will be analysis of the primary endpoint on the ITT population (see section 4.8).

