4.1 General Statistical Considerations

Individual data listings will be provided for all subjects enrolled, sorted by treatment group, site, subject and time point. Summary tables will be presented for the safety population by treatment group.

Descriptive statistics for continuous variables will be number of subjects (N), mean (Mean), standard deviation (SD), median (Median), minimum (Min) and maximum (Max). For categorical variables, the absolute (N) and relative frequency

(%) will be tabulated. Confidence intervals (CI) for mean values will be added if appropriate.

The analyses of the primary and key secondary efficacy endpoint are described in sections 4.8.1 and 4.8.2.

Due to early termination of the study, the sample size will be much less than planned. As a result, the statistical power can be inadequate for the planned gatekeeping methodology. Therefore, standard hypothesis testing methods may be used instead to analyze the data.

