4.8 Efficacy Analysis

The primary and key secondary analyses will be completed for the ITT and PP populations.

Due to early termination of the study, the sample size will be much less than planned. As a result, the statistical power can be inadequate for the planned gatekeeping methodology. Therefore, standard hypothesis testing methods may be used instead to analyze the data.

[figure not shown]
To account for these possibilities and to facilitate better understanding of the data, the data will be analyzed 'as planned' in the protocol AND using more simple, unadjusted alpha analyses with basic chi-square tests. Therefore the data (Table 8A and 8B) will be analyzed two ways:

- Original Primary and Key Secondary Analyses using Hochberg's procedure and gatekeeping methods
- Modified Primary and Key Secondary Analyses using simple chi-square tests.

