4.8.1.2 Key Secondary Analyses

The three key secondary endpoints are: 1) EULAR response (good) rate at Day 8, 2) EULAR response (good and moderate combined) rate at Day 15, and 3) EULAR response (good) rate at Day 15. Both comparisons (Nanocort 150 mg vs. Depo-Medrol[®], and Nanocort 75 mg vs. Depo-Medrol[®]) will be completed for each of the three key secondary endpoints (i.e., up to 6 key secondary analyses).

The key secondary hypotheses will only be tested if at least one primary analysis is significant. If for one of the dosages the primary analyses is not significant, then the corresponding key secondary hypotheses will not be tested. The key secondary hypotheses will be tested with a two-sided confidence level, α_s . The calculation of α_s depends on the maximum p-value from the primary hypotheses, the significance of the primary hypotheses and α_p .

Step 1: The primary hypotheses are tested using Hochberg procedure at $\alpha_p = 0.045 < \alpha$ (0.05). If at least one of the primary null hypotheses is rejected then go to Step 2. The significance value for Step 2 (α_s) is a function of largest primary p-value.

Step 2: Test the secondary null hypotheses using Hochberg procedure at α_s .

$$\begin{aligned}\alpha_s &= \min(\lambda \alpha^*/(p^*)^2, \alpha_p) && \text{if } p^* > \alpha_p \text{ and} \\ \alpha_s &= \alpha && \text{if } p^* \leq \alpha_p\end{aligned}$$

[figure not shown]
Where p^* is the largest primary p-value, λ is chosen to control the global FWER at the alpha level.

$$\begin{aligned}\alpha^* &= \alpha_p(1 - \sqrt{2 - \alpha_p/(k_1 - 1)} - \alpha / \alpha_p)^2 && \text{if } \alpha' \leq \alpha \\ &= \alpha_p(\alpha - \alpha_p) / (k_1 - 1 - \alpha_p) && \text{if } \alpha' > \alpha\end{aligned}$$

Where $\alpha' = \alpha_p + \alpha_p^2 / (k_1 - 1) - \alpha_p^3 / (k_1 - 1)^2$

K_1 = Number of primary endpoints (in this case $k_1 = 2$)

The significance level carried over to α_s depends on the magnitude of the primary p-values rather than the number of significant primary p-values. This method assumes a full parametric model. The joint distribution of the hypotheses in primary and secondary endpoints is considered to calculate λ . If the joint distribution of the test statistic is not specified, the λ parameter is chosen under the worst-case scenario.

The key secondary analyses will be completed for the ITT and PP populations.

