4.8.2 Simplified Analyses

The primary and key secondary analyses will be completed using the Hochberg and gatekeeping methodology described above but will also be analyzed using simple chi-square tests.

The simplified analyses will be completed for the ITT and PP populations.

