4.11 Modifications from the statistical section in the protocol

The protocol stated hypotheses with one-sided testing using less than and greater than symbols. This is corrected in the SAP to two-sided hypotheses, as planned, using equal and not equal symbols.

The protocol stated that Cochrane-Mantel-Haenszel test stratified by study site will be used for the primary analysis. However, this conflicts with the primary and key secondary hypotheses planned in the protocol which are not stratified, so this is revised in the SAP to match with the planned hypotheses.

Due to early termination of the study, the sample size will be much less than planned. As a result, the statistical power can be inadequate for the planned

gatekeeping methodology. Therefore, standard hypothesis testing methods may be used instead to analyze the data (see section 4.8).

5. Interim analyses

No interim analyses were planned.

6. Sample size and Power calculations

A total of 330 subjects were to be enrolled and randomized into 3 groups (1:1:1).

The EULAR response rate will be considered as primary parameter. See Appendix B for details on scoring and coding. There is a special interest in the percentage of subjects with an EULAR response category of good or moderate (good and moderate combined) and the percentage of subjects with an EULAR response category of only good. These subjects will be called EULAR responders and EULAR good-responders, respectively.

[figure not shown]

Primary endpoint:

- The percentage of EULAR responders (good + moderate) at Day 8

Key secondary endpoints:

- The percentage of EULAR good responders at Day 8
- The percentage of EULAR responders at Day 15
- The percentage of EULAR good responders at Day 15

[REDACTED]

[REDACTED]
[REDACTED]
[REDACTED]
[REDACTED]
[REDACTED]
[REDACTED]

The sample size calculation is based on estimates from [REDACTED]

[REDACTED]
[REDACTED]
[REDACTED]
[REDACTED]
[REDACTED]
[REDACTED]
[REDACTED]
[REDACTED]
[REDACTED].

Although the above described the planned sample size, the study enrollment did not reach the planned goal, and the study may likely have inadequate statistical power.

7. Tables, Listings and Figures

Below are the titles for the planned study tables, listings and figures

Table 1	Subject Distribution
Table 2.A	Subject Distribution By Center (ITT)
Table 2.B	Subject Distribution By Center (PP)
Table 3.A	Demographics and Baseline Characteristics (ITT)
Table 3.B	Demographics and Baseline Characteristics (PP)

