Table 4	Medical and Surgical History (ITT)
Table 5.A	Dose Administration (ITT)
Table 5.B	Dose Administration (PP)
Table 6.A	Dose Administration by Visit (ITT)
Table 6.B	Dose Administration by Visit (PP)
Table 7.A	Dose Administration by Center (ITT)
Table 7.B	Dose Administration by Center (PP)
Table 8.A	EULAR Good/Moderate Responders - Original and Simplified Analyses (ITT)
Table 8.B	EULAR Good/Moderate Responders - Original and Simplified Analyses (PP)
Table 9.A	EULAR Response by Visit (ITT)
Table 9.B	EULAR Response by Visit (PP)
Table 10.A	Time to First EULAR Good/Moderate Response (ITT)
Table 10.B	Time to First EULAR Good/Moderate Response (PP)
Table 11.A	DAS28 Scores (ITT)
Table 11.B	DAS28 Scores (PP)
Table 12.A	Tender and Swollen Joints (ITT)
Table 12.B	Tender and Swollen Joints (PP)
Table 13.1.A	Visual Analog Scale (VAS) – Patient Pain (ITT)
Table 13.1.B	Visual Analog Scale (VAS) – Patient Pain (PP)
Table 13.2.A	Visual Analog Scale (VAS) – Patient RA Disease Activity (ITT)
Table 13.2.B	Visual Analog Scale (VAS) – Patient RA Disease Activity (PP)
Table 13.3.A	Visual Analog Scale (VAS) – Investigator RA Disease Activity (ITT)
Table 13.3.B	Visual Analog Scale (VAS) – Investigator RA Disease Activity (PP)
Table 14.A	American College of Rheumatology (ACR) 20/50/70 Response (ITT)
Table 14.B	American College of Rheumatology (ACR) 20/50/70 Response (PP)
Table 15.1.A	SF-36 Physical Component Score (ITT)
Table 15.1.B	SF-36 Physical Component Score (PP)
Table 15.2.A	SF-36 Mental Component Score (ITT)

Table 15.2.B	SF-36 Mental Component Score (PP)
Table 16.A	Health Assessment Questionnaire (HAQ) (ITT)
Table 16.B	Health Assessment Questionnaire (HAQ) (PP)
Table 17.A	Functional Assessment of Chronic Illness Therapy (FACIT) Fatigue Score (ITT)
Table 17.B	Functional Assessment of Chronic Illness Therapy (FACIT) Fatigue Score (PP)
Table 18	Maintenance Improvement at Week 12 (Day 85)
Table 19.A	Health Economics Questionnaire (HEQ) at Week (Day 85) (ITT)
Table 19.B	Health Economics Questionnaire (HEQ) at Week (Day 85) (PP)
Table 20.A	Laboratory Results (SAF)
Table 20.B	Laboratory Abnormalities (SAF)
Table 20.C	Laboratory Shift (SAF)
Table 21	Vital Signs (SAF)
Table 22	Physical Exam (SAF)
Table 23	12-Lead ECG (SAF)
Table 24.A	Concomitant Medications Summary (SAF)
Table 24.B	Concomitant Medications (SAF)
Table 25.A	Adverse Event Summary (SAF)
Table 25.B	Adverse Events
Listing 1	Subject Disposition

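### The SAP runs a Hochberg/gatekeeping analysis and an unadjusted chi-square analysis without saying which decides study success; if the unadjusted one may decide, the false-positive risk is about 9.1% instead of 4.3%

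*Combined protocol and SAP*

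**What the plan says.** **The success rule.** Protocol section 4.4 has two primary null hypotheses, one per Nanocort dose against Depo-Medrol, and calls the study positive if one of them is rejected. SAP section 2.1 ties study success to the primary endpoint in the ITT population and points to section 4.8 for the method.

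**What section 4.8 holds.** It contains two analyses of the same endpoints:

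- The original analysis (4.8.1): two-sided hypotheses, Hochberg on the two primary tests at 0.045 within an overall 0.05, then key secondary tests at a level that depends on the larger primary p-value. A constant, lambda, "is chosen to control the global FWER at the alpha level".
- A second analysis "using more simple, unadjusted alpha analyses with basic chi-square tests", listed as "Modified Primary and Key Secondary Analyses using simple chi-square tests". Section 4.8.2 confirms that the endpoints "will also be analyzed using simple chi-square tests".

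**How the two relate.** Sections 4.8 and 4.8.2 say both will be run, and Tables 8.A and 8.B in SAP section 7 report them together. Yet sections 4.1, 4.8 and 4.11 each say, on grounds of low power: "Therefore, standard hypothesis testing methods may be used instead to analyze the data". By contrast, section 2.2 explicitly ranks the per-protocol analyses as supportive. The chi-square set receives no such label anywhere in the visible text.

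**The concern.** The SAP describes the unadjusted tests both as an addition to the planned analysis and as a possible replacement for it. The only sentence on study success points to a section holding both. Whoever writes the report can therefore choose the deciding analysis after seeing the p-values.

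That choice can change the answer. Section 4.8.1.1 names no test statistic and section 4.11 drops the site stratification, so the main visible difference between the two sets is the multiplicity adjustment. A win that appears only in the simple set would come from a looser threshold and not from a better analysis. Low power does not justify this, because the simple tests gain power only by spending more alpha.

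The key secondary claims are exposed too. Under the original plan a dose that fails its primary test has its key secondary hypotheses left untested. Under the simple set all six key secondary tests can be read without a gate.

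**Working it through.** **Inputs**

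- Two primary comparisons sharing one control arm; two-sided (SAP 4.8.1.1, 4.11).
- Hochberg level 0.045, overall alpha 0.05 (SAP 4.8.1.2).
- Positive study if either null is rejected (Protocol 4.4).
- Allocation 1:1:1 (Protocol 8.2). With equal arms each contrast has variance 2σ²/n and the two share covariance σ²/n from the control, so their correlation is 1/2.
- Assumed: 0.05 two-sided per simple test, and no true difference between any arms.

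**Step 1: reproduce the SAP's 0.045.** With two tests, Hochberg rejects at least one null if the smaller p ≤ 0.0225 or the larger p ≤ 0.045. For independent tests:

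- P(smaller p ≤ 0.0225) = 1 − (1 − 0.0225)² = 0.04449
- P(both p between 0.0225 and 0.045) = 0.0225² = 0.00051
- Sum = 0.0450, as stated.

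**Step 2: the shared control.** Bivariate normal, correlation 0.5:

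- Hochberg at 0.045: P(smaller p ≤ 0.0225) = 0.0420, plus P(both between 0.0225 and 0.045) = 0.0013, total **0.0433**. The same rule at 0.05 gives 0.0480.
- Unadjusted: 1 − P(|Z₁| < 1.96 and |Z₂| < 1.96) = **0.0907**.
- Ratio: 0.0907/0.0433 = 2.1 (1.9 against Hochberg at 0.05).

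**Step 3: if either set may decide.** Any Hochberg rejection at 0.045 has p ≤ 0.05, so with the same p-values its rejection region lies inside the unadjusted one. Letting either set decide therefore also costs 9.1%.

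**Step 4: where the verdicts conflict.** The unadjusted set rejects and Hochberg does not when 0.0225 < smaller p ≤ 0.05 and larger p > 0.045. With no true difference this has probability 0.0907 − 0.0433 = 0.047.

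**Step 5: sensitivity**

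| Setting | Unadjusted | Hochberg at 0.045 |
|---|---|---|
| Correlation 0 | 9.75% | 4.50% |
| Correlation 0.5 | 9.1% | 4.3% |
| Correlation 0.7 | 8.3% | 4.1% |
| Exact binomial, Pearson chi-square, 20–60 per arm, common rate 40–70% (assumed) | 7.7–10.3% | 3.9–5.2% |
| Counting only rejections favouring Nanocort, correlation 0.5 | 4.5% | 2.2% |

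At 0.045 per simple test instead of 0.05, the unadjusted figure is 8.2%. The achieved sample size is not given; the binomial row shows that the result does not hinge on it.

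**Step 6: the key secondary level.** From SAP 4.8.1.2 with k₁ = 2:

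- α′ = 0.045 + 0.045² − 0.045³ = 0.0469, which is ≤ 0.05, so the first branch applies.
- α* = 0.045 × (1 − √(2 − 0.045 − 0.05/0.045))² = 0.000298
- When the larger primary p-value p* exceeds 0.045, α_s = min(λα*/p*², 0.045).

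No value of lambda is visible. For two assumed values:

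| p* | α_s if λ = 1 | α_s if λ = 10 |
|---|---|---|
| 0.10 | 0.030 | 0.045 |
| 0.20 | 0.0074 | 0.045 |
| 0.50 | 0.0012 | 0.012 |

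The simple tests would use 0.05 each, with no gate.

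**The case against.** The best reply is that the SAP all but settles the matter. After the substitution sentence, section 4.8 says both analyses will be run, to help understanding of the data. Only section 4.8.1 sets out hypotheses, a level and a rejection rule, and it carries the label of the original analysis. The Hochberg result will always be reported, and the SAP is open about low power. On this reading only one ranking sentence is missing. The inference is reasonable, but it remains an inference: the substitution sentence appears three times and contradicts it, and the second set is labelled as a modified primary analysis.

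Three technical points deserve an answer:

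- *Direction.* The 9.1% counts rejections against Nanocort as well, although the aim is superiority. Counting only favourable rejections halves both figures, to 4.5% and 2.2%, and leaves the ratio at 2.1. The two-sided count follows the hypotheses and the success rule as written.
- *Same p-values.* Steps 3 and 4 assume both sets use the same test. Protocol section 10.2 planned a site-stratified test, but SAP section 4.11 drops the stratification, and Protocol section 10.1 names chi-square or Fisher's exact test for binary data. If the tests did differ, the conflict zone would not be exact, and letting either set decide could only raise the error above the unadjusted figure.
- *Redaction.* Parts of SAP section 6 are blacked out, so the finding concerns the visible text only.

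Lambda is a fair side issue. The SAP says how it is to be chosen, including a worst-case rule, and a figure is missing nearby. The main conclusion does not depend on it.

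**Conclusion.** The concern holds. The visible SAP allows an unadjusted analysis to stand in for the error-controlled one and gives no rule for choosing between them, while success depends on either dose winning. If the unadjusted tests may decide, the chance of a falsely positive study is about 9.1% against 4.3% under the SAP's own Hochberg rule, a factor of 2.1. This rests on 0.05 two-sided per simple test, equal arms and no true difference. The absolute figures move with those assumptions, but the roughly twofold increase persists in the direction count and across the correlations examined. In the exact binomial calculations the ratio ranges from 1.8 to 2.6. This must be fixed before unblinding, because the ambiguity bears directly on the main conclusion.

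**What to change.** Before unblinding:

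1. Delete the sentence permitting substitution in SAP sections 4.1, 4.8 and 4.11.
2. State in sections 2.1 and 4.8 that study success and all key secondary claims rest only on the Hochberg/gatekeeping analysis in the ITT population.
3. In sections 4.8 and 4.8.2, drop the label that presents the chi-square set as modified primary and key secondary analyses. Call those results descriptive: estimates, 95% confidence intervals and nominal p-values, with no claim of significance. Label Tables 8.A and 8.B to match.
4. As a lesser item, give the value of lambda in section 4.8.1.2, so that the key secondary level can be computed when the larger primary p-value exceeds 0.045.

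The cost is SAP wording and deriving lambda once. No data collection changes. The sponsor gives up the option of resting a claim on a nominal chi-square p-value.

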4.2 Missing Data Handling

Imputation will be implemented for partial start/end dates of adverse events dates. If the start day is missing, impute the 1st of the month, unless month and year are the same as month and year of the first dose of study drug then impute the first dose date. If start day and start month are both missing, impute 1st January but if year is the same as year of the first dose date, then impute first dose date. If the end day is missing, impute the last day of the month. If end day and end month are both missing impute 31st December. No other imputation of missing data will be performed, and only available data will be presented.

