8.3 Study procedures

The Schedule of Assessments (Table 2) included in the protocol summarizes the timing of the efficacy and safety measurements.

The Day of the first dose administered to a subject is considered Day 1 for that individual subject. Other study Days are calculated with Day 1 as the reference point. Screening will consist of period up to 2 Weeks (14 Days) and those subjects that are still eligible after the screening visit will be randomized to one of the three treatment groups.

Treatment will be given on Day 1 and Day 15. The patient will be followed up for 12 Weeks or End of Study visit. In the event of early termination, subjects are asked to return for the Week 12 assessments if possible. Otherwise, the subjects are assessed as per Week 12 assessment schedule on the Day of termination. Infusion related reactions will be monitored during the infusion and at the end of infusion.

Physical Examination

A full physical examination should include: General appearance, Skin, Head and Neck, Eyes-Ears-Nose, Throat, Lymph Nodes palpation, Cardiovascular, Lungs & Chest, Abdomen, Musculoskeletal, and Neurological Function. All other body systems should be assessed at the Investigator's discretion. A full physical examination will be done at Screening, Baseline

and End of study. For remaining visits it will be up to the judgement of the Investigator if a full or abbreviated exam is completed.

Vital Signs

Vitals signs will be taken supine (for 5 minutes) and include heart rate, respiratory rate, blood pressure (BP), and temperature. The method of temperature assessment must remain consistent for each individual subject throughout the study.

Subject blood pressure and heart rate will be measured using an automatic device (whenever possible) after the subject has rested (supine) comfortably for 5 min. Vital signs will be measured at the time points specified in the Schedule of Assessments (Table 2).

Weight will be recorded as per Table 2.

Disease Activity Score in 28 Joints (DAS28)

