10.8 Analysis Populations

The following analysis populations will be defined:

Intent to treat (ITT) population

All subjects randomized will be included in the ITT population, if:

- At least one dose of study medication was administered

Subjects will be assigned to treatment groups as randomized for analysis purposes.

Per protocol (PP) population

The per-protocol population will be defined as the subset of the ITT population without the following exclusions:

- Major violation of inclusion or exclusion criteria
- Withdrawal from the study before week 2
- Other major protocol violations, such as use of prohibited medication

Details will be described in the data review plan. Subjects will be assigned to treatment groups as treated for analysis purposes.

Safety (SAF) population

All subjects randomized will be included in the SAF population, if:

- At least one dose of study medication was administered and
- At least one post randomization safety assessment was performed.

Subjects will be assigned to treatment groups as treated for analysis purposes.

Since the primary endpoint is EULAR response on Day 8, those subjects who had received the first dose on Day 1 and EULAR response is assessed will be considered for primary endpoint analysis as these patients are fulfilling the requirement for primary endpoint assessment. Secondary endpoints are also assessed depending on the dataset available by which the particular endpoint can be calculated.

A list of protocol violations leading to exclusion from the PP population will be finalized before database lock. During the blind data review before database lock the PP population will be defined.

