10.9 Missing Data

The handling of missing data for the clinical endpoints will be discussed in detail in the SAP.

For the primary endpoint EULAR response on Day 8, subjects who withdraw from the study before Day 8, because of insufficient efficacy will be considered as non-responders.

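### SAP 4.2 drops, without saying so, the protocol 10.9 rule that counts withdrawals before Day 8 for insufficient efficacy as non-responders; the SAP's ITT and PP sets also differ from the protocol supplied, and SAP 4.11 lists none of this

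*Combined protocol and SAP*

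**What the plan says.** **Missing data.** Protocol 10.9 leaves the detail to the SAP ("The handling of missing data for the clinical endpoints will be discussed in detail in the SAP") and then fixes one rule for the Day 8 primary endpoint: "subjects who withdraw from the study before Day 8, because of insufficient efficacy will be considered as non-responders". Protocol 10.8 points the other way, since "those subjects who had received the first dose on Day 1 and EULAR response is assessed will be considered for primary endpoint analysis". SAP 4.2 imputes partial adverse event dates and ends "No other imputation of missing data will be performed, and only available data will be presented". The non-responder rule is not in SAP 4.8.1, 4.8.2, 4.8.3 or Appendix B. SAP 4.8.3 also makes DAS28 missing whenever one of its four components is missing.

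**ITT set.** Protocol 10.8 requires randomisation and at least one dose. SAP 2.1 adds the condition that "at least one post-baseline efficacy measurement was performed".

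**PP set.** Protocol 10.8 excludes for "Withdrawal from the study before week 2". SAP 2.2 lists withdrawal before week 12 among conditions that would probably lead to exclusion. SAP section 2 uses the PP set to confirm the ITT findings on the primary and key secondary endpoints, all of which fall at Day 8 or Day 15.

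**Declared changes.** SAP section 4 undertakes to document any difference from the protocol, which it names as V3.1. SAP 4.11 lists three: sidedness of the hypotheses, removal of site stratification from the primary test, and early termination.

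**The concern.** A subject who leaves in the first week because treatment has not worked is a failure under protocol 10.9. Under SAP 4.2 that subject has no Day 8 response and drops out of both numerator and denominator. If such losses differ between arms, the responder-rate comparison shifts in favour of the arm that lost more failures, which could be Nanocort or Depo-Medrol.

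The ITT change matters once the rule is restored: a subject who left with no post-baseline efficacy measurement would still be outside the analysis set.

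The PP change is a separate problem. A week 12 cut-off can remove subjects from the Day 8 and Day 15 analyses because of events after those visits, which weakens the PP analysis as confirmation.

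Because none of this is declared, a reader of the report could not tell that the denominator differs from the one in protocol 10.9.

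**Working it through.** The plan gives no figure of its own to reproduce here. The planned size is 3 × 110 = 330, and the responder rates in SAP section 6 are blacked out. The check is a comparison of text, followed by illustrations on **assumed** counts.

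**1. Text side by side**

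| Item | Protocol supplied | SAP | Listed in SAP 4.11? |
|---|---|---|---|
| Withdrawal before Day 8, insufficient efficacy | Non-responder (10.9) | Not imputed, available data only (4.2) | No |
| ITT | Randomised and dosed (10.8) | Adds a post-baseline efficacy measurement (2.1) | No |
| PP withdrawal cut-off | Week 2 (10.8) | Week 12 (2.2) | No |

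**2. Effect of omitted failures on one arm's rate.** With n subjects, 50% response (assumed) and k failures omitted, the shift is 0.5n/(n − k) − 0.5.

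| n per arm | k = 1 | k = 2 |
|---|---|---|
| 110 (planned) | 55/109 − 0.5 = 0.46 points | 55/108 − 0.5 = 0.93 points |
| 50 (assumed) | 25/49 − 0.5 = 1.02 points | 25/48 − 0.5 = 2.08 points |
| 30 (assumed) | 15/29 − 0.5 = 1.72 points | 15/28 − 0.5 = 3.57 points |

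**3. Effect on the test.** Pearson chi-square without continuity correction, χ² = N(ad − bc)²/[(a+b)(c+d)(a+c)(b+d)], Nanocort first. For 29/50 vs 20/50, χ² = 100 × 450²/(50 × 50 × 49 × 51) = 3.24. With two Nanocort failures omitted, χ² = 98 × 490²/(48 × 50 × 49 × 49) = 4.08.

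The unadjusted limit is 0.05 (simplified analysis, SAP 4.8.2). In the Hochberg analysis of SAP 4.8.1.2 at 0.045, one dose alone needs p ≤ 0.045/2 = 0.0225 when the other dose has p > 0.045. SAP 4.8.1 names no test statistic for that analysis, so chi-square is assumed there.

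| Limit | Failures counted (10.9) | Failures omitted (SAP 4.2) |
|---|---|---|
| 0.05 | 29/50 vs 20/50, p = 0.072 | 29/48 vs 20/50, p = 0.043 |
| 0.05 | 30/50 vs 20/50, p = 0.046 | 30/50 vs 20/49, p = 0.056 |
| 0.0225 | 31/50 vs 20/50, p = 0.0278 | 31/49 vs 20/50, p = 0.0206 |
| 0.0225 | 32/50 vs 20/50, p = 0.0163 | 32/50 vs 20/48, p = 0.0268 |

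In each pair, one or two subjects change the decision. The first and third move towards significance, the second and fourth away from it.

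**4. PP cut-off.** Week 12 is Day 85, so exclusion can depend on follow-up (85 − 8)/7 = 11 weeks after the primary endpoint and (85 − 15)/7 = 10 weeks after the Day 15 endpoints. As an extreme case, take 50 in an arm with 25 Day 8 responders, and let 5 (the approximate 10% overall drop-out of protocol 4.4) leave after Day 15. The PP Day 8 rate becomes 20/45 = 44.4% if all five were responders and 25/45 = 55.6% if none were, against 50% before.

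**The case against.** **The conflict starts inside the protocol.** Protocol 10.8 limits the primary analysis to assessed subjects, 10.9 counts some unassessed ones, and 10.9 hands missing data to the SAP. On this view the SAP chose one side and dropped nothing. That is fair as far as it goes. But 10.9 delegates detail and fixes this rule in its next sentence, so leaving it out is a choice the SAP should state.

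**The protocol supplied may not be V3.1.** SAP 4.11 attributes one-sided hypotheses to the protocol, whereas protocol 4.4 states equalities. SAP 1.1 also words the flare definition differently. This stands: the omissions from 4.11 are established only against the text supplied. The texts do overlap, because the site-stratified test that 4.11 attributes to the protocol is in protocol 10.2.

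**The ITT and PP points are secondary.** The ITT condition bites only once 10.9 is restored, and only for subjects with no post-baseline assessment. Protocol 8.3 intends an assessment even for early leavers: "Otherwise, the subjects are assessed as per Week 12 assessment schedule on the Day of termination". The PP analysis is supportive, also serves endpoints up to week 12, and has its final criteria in a separate document. All of this stands and limits the weight of both points.

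**Few subjects, and chosen counts.** The rule covers one week and one reason, and protocol 5.2.4 keeps week 2 non-responders in the study. The illustrations sit near the limits, with losses in one arm only. With Fisher's exact test, which protocol 10.1 allows generally, the four pairs become 0.109 to 0.068, 0.071 to 0.071, 0.045 to 0.027 and 0.027 to 0.042, and none crosses its limit. The crossings therefore depend on the test, although SAP 4.8.2 does specify chi-square for the simplified analysis. The rate shifts in step 2 do not depend on the test.

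**Conclusion.** The concern holds. Followed as written, the SAP removes from the Day 8 denominator failures that protocol 10.9 counts, and it does not say so. It also narrows the ITT set and lets the PP set select Day 8 and Day 15 results on later events.

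The likely size is small in subjects: about 0.5 to 1.7 points on one arm's rate per omitted failure at 110 to 30 per arm, assuming 50% response. The direction is unknown. It could decide a borderline result, and SAP 4.1 expects a sample well below plan, so each such subject weighs more than at 110 per arm. The documents give no withdrawal counts, and the p-values rest on assumed counts and uncorrected chi-square.

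No Day 15 rule is claimed. Protocol 10.9 covers Day 8 only, and under 10.8 "Secondary endpoints are also assessed depending on the dataset available by which the particular endpoint can be calculated". This should be fixed, with medium confidence because of the version question.

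**What to change.** Before unblinding:

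- **SAP 4.2:** state that withdrawal before Day 8 for insufficient efficacy is non-response for the primary endpoint, and that this takes precedence over the assessed-response sentence in protocol 10.8.
- **SAP 2.1:** use the protocol's ITT set (randomised and dosed) and delete the post-baseline efficacy condition.
- **SAP 2.2 and the blinded-review document:** for the Day 8 and Day 15 PP analyses, return to the week 2 cut-off, or use one tied to each endpoint visit and declare it in SAP 4.11.
- **Sensitivity analyses:** report the Day 8 result on available cases, and with every missing response counted as non-response. The second should not be primary, because one missing DAS28 component could turn a responder into a failure.
- **SAP 4.11:** check against protocol V3.1 and list every difference that remains. Extending the non-responder rule to Day 15 is optional and would be a new rule to declare.

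The cost is wording in the SAP and the blinded-review document plus two further analysis runs. Precedence is settled in the SAP, so no protocol amendment is asked for. Reported Day 8 response rates may be slightly lower.
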